9.4.2 Study Data

Cognitive function will be determined with a neuropsychological battery designed to evaluate 7 cognitive domains including: attention, concentration, working memory, executive function; visuospatial/visuoconstructive skills; naming/semantic memory; and verbal and nonverbal episodic memory. Neuropsychological tests and corresponding cognitive skills are the following:

- 1) Symbol Digit Modalities Test
- 2) Trail Making Test, Part B
- 3) Shipley Institute of Living Scale, Abstraction scale
- 4) Letter-Number Sequencing
- 5) Block Design
- 6) Judgment of Line Orientation
- 7) Animal Naming
- 8) Boston Naming Test
- 9) California Verbal Learning Test
- 10) East Boston Memory Test
- 11) Faces I and II
- 12) Benton Visual Retention Test
- 13) Stroop Color and Word Test
- 14) Wechsler Test of Adult Reading (verbal intelligence quotient)

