9.4.3 Data Collection Schedule

Cognitive assessments will be performed at v00 (baseline) and at study visits v18 and v36.

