9.6.5.3 Secondary Efficacy Analysis: Cognition Analyses

Three composite cognitive measures will be used to test for randomized treatment group differences in cognition; each composite will be considered as co-secondary endpoints. (1) The global composite will use scores from all neuropsychological tests. (2) The verbal memory composite will use the California Verbal Learning Test and East Boston Memory Test immediate and delayed recall scores. (3) The executive function composite (determined from principal components of prior trial data) will use scores from the Symbol Digit Modalities Test, the Trail Making Test, the Shipley Abstraction scale, Letter-Number Sequencing, and category fluency. The composites will be calculated as the average of component standardized scores weighted by the inverse interest correlation matrix. Absolute values of change from baseline on each cognitive endpoint will be calculated at both post-randomization cognitive follow-ups (18 and 36 months). General estimating equation models will be used to analyze the repeated measures of change in the cognitive endpoints. The primary independent variables will be randomized treatment group; covariates will include the CIMT randomization stratification variable as well as the baseline value of the cognitive endpoint. Differences in cognitive change will be tested by treatment group. Further analyses will test for interactions with test time (18 versus 36 months) to evaluate whether treatment effects (treatment by time interaction) vary by follow-up time.

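### As worded, the global cognitive change composite includes a reading-based verbal-IQ test that lies outside the battery's stated domains

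*Combined protocol and SAP*

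**What the plan says.** Section 9.6.5.3 sets up the secondary analysis: "Three composite cognitive measures will be used to test for randomized treatment group differences in cognition; each composite will be considered as co-secondary endpoints".

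- **Global composite:** "The global composite will use scores from all neuropsychological tests". No test is excepted.
- **Verbal memory composite:** "The verbal memory composite will use the California Verbal Learning Test and East Boston Memory Test immediate and delayed recall scores".
- **Executive composite:** it "will use scores from the Symbol Digit Modalities Test, the Trail Making Test, the Shipley Abstraction scale, Letter-Number Sequencing, and category fluency".
- **Scoring:** "The composites will be calculated as the average of component standardized scores weighted by the inverse interest correlation matrix". I read the word before the correlation matrix as a slip for inter-test.

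Section 9.4.2 describes the battery as covering seven domains: "attention, concentration, working memory, executive function; visuospatial/visuoconstructive skills; naming/semantic memory; and verbal and nonverbal episodic memory". It then lists 14 tests. The fourteenth is "Wechsler Test of Adult Reading (verbal intelligence quotient"; it is the only entry labelled as an IQ measure.

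Section 9.4.3 gives one schedule for the whole battery: "Cognitive assessments will be performed at v00 (baseline) and at study visits v18 and v36". It does not limit any test to baseline.

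**The concern.** The three sections together put the reading test into the global composite and have it repeated at 18 and 36 months. The outcome is change in cognition under treatment, and the other 13 tests are there to measure the named domains. The plan gives the reading test a different role, an IQ estimate, and verbal IQ is not a named domain.

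A component that does not move with treatment pulls the composite's between-arm difference toward zero by its share of the weight. Under the specified weighting that share is not fixed at one fourteenth. Inverse-correlation weights favour tests that correlate less with the rest, so a test that stands apart from the battery can receive well above an equal share. At stake are the size and interpretability of the estimate for one of three co-secondary measures.

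**Working it through.** The documents give no effect size, standard deviation, correlation or power for cognition, so there is no stated figure to reproduce. What follows is illustrative.

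**Inputs from the plan:** 14 tests; standardized scores; inverse-correlation weights, taken as w proportional to R⁻¹·1.

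**Assumptions:** equal true benefit on 13 tests and none on the reading test; correlation 0.4 among the 13; correlation q between the reading test and each of the others.

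**Step 1. Weight share of the reading test.** Let a be the weight of each of the 13 tests and b that of the reading test. Solving R·w = 1:

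- (1 + 12×0.4)a + q·b = 1 and 13q·a + b = 1
- so a = (1 − q)/(5.8 − 13q²), b = 1 − 13q·a, share s = b/(13a + b)

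| q | a | b | s |
|---|---|---|---|
| 0.4 | 0.161 | 0.161 | 0.071 |
| 0.3 | 0.151 | 0.410 | 0.173 |
| 0.2 | 0.152 | 0.606 | 0.235 |

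Equal weights give s = 1/14 = 0.071. The share falls below 7% when q exceeds 0.4 and reaches zero at q = 5.8/13 = 0.446. It is therefore sensitive to a correlation the plan does not give.

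**Step 2. Raw dilution.** The composite effect is (1 − s) times the 13-test effect. The raw loss equals s: 7%, 17% or 24%.

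**Step 3. Standardized effect.** A reading score that changes little also adds little noise, so the signal-to-noise loss is smaller. Let v be the change variance of each of the 13 tests, u that of the reading test, ρ the correlation among the 13 change scores, and ρᵣ that between reading change and each of the others.

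- V = v(1 + 12ρ)/13
- ratio to the 13-test value = (1 − s)√V / √[(1 − s)²V + s²u + 2s(1 − s)ρᵣ√(vu)]

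Assume a retest correlation of 0.75 for the 13 tests, so v = 2(1 − 0.75) = 0.5. For reading assume 0.95 or 0.90, so u = 0.1 or 0.2. Take ρ = 0.1 or 0.3, and ρᵣ = 0 or equal to ρ.

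- *Smallest loss at s = 0.071* (ρ = 0.3, u = 0.1, ρᵣ = 0): V = 0.1769; ratio = 0.3906/√(0.15255 + 0.00051) = 0.998, a loss of 0.2%.
- *Largest loss at s = 0.071* (ρ = 0.3, u = 0.2, ρᵣ = 0.3): 4.2%.
- *Smallest loss at s = 0.235* (ρ = 0.3, u = 0.1, ρᵣ = 0): 2.6%.
- *Largest loss at s = 0.235* (ρ = 0.1, u = 0.2, ρᵣ = 0.1): V = 0.0846; ratio = 0.2224/√(0.04948 + 0.01107 + 0.01138) = 0.829, a loss of 17.1%.

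Rounded, this is 0–4% and 3–17%.

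**Step 4. Power illustration at the 1/14 share.** Assume 120 per arm, two-sided 0.05, benefit 0.2 baseline SD, change SD 0.7 and all correlations 0.5. Power is 85.5% with 13 tests. It is 84.7% with a very stable reading score (change SD 0.1) and 80.2% with one as variable as the other tests (change SD 0.7).

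**Step 5. Reach.** The verbal memory composite names two tests and the executive composite five. The reading test is in neither.

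**The case against.** The strongest reply is that the premise comes from outside the plan. The documents call the test a verbal intelligence quotient; they do not say it is stable or insensitive to treatment. That stands, and every size above is conditional on it. What the documents do show is that the test is listed, not excepted, and outside the stated domains.

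A second reply is that the practical loss is small. At an equal share and with a stable score, it is about 1% or less in standardized effect and under one percentage point of power. That stands too. The larger figures need the reading test to correlate only about 0.2 with the battery, which is undocumented; at 0.446 it would receive no weight at all.

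A third is that dropping the test, or adding it as a covariate, is partly preference, since the models already adjust for the baseline value of each cognitive end point. This is fair as to the covariate, which is optional.

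A reader might infer more than the text supports:

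- **That the reading test cannot show decline.** Nothing in the documents says so.
- **That the formula combines tests without aligning their direction,** so that a time-scored test such as Trail Making partly cancels the others. Section 9.6.5.3 says nothing either way, and no scoring direction is given for any test. Sections 9.4.1 and 9.4.4 refer to a summary score form and a protocol for summarizing the cognitive data, neither of which is reproduced here, and orientation may be set there. A reversed component would do serious damage under inverse-correlation weights, but that is a hypothetical case.
- **That the secondary end point as a whole understates any treatment effect.** The reading test is in one of three composites, and even there the dilution is conditional.

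**Conclusion.** The point holds in a limited form. On the literal text, the global change composite includes a verbal-IQ reading test that belongs to none of the battery's stated domains. If that score does not respond to treatment, the raw global effect is diluted by about 7% with equal weights, and by 7–24% with inverse-correlation weights when its correlation with the other tests runs from 0.4 down to 0.2. The standardized loss is about 0–4% at the lower share and 3–17% at the upper, under the retest and change-score correlations assumed above. Confidence is high on the wording and moderate on the size. The gain from correcting it is real but modest, and limited to one of three co-secondary measures. Score orientation is a matter for clarification and not a demonstrated error.

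**What to change.** In section 9.6.5.3, state that the global composite uses the 13 tests other than the Wechsler Test of Adult Reading, and that the reading score is kept as a baseline descriptor or, optionally, a covariate in the cognition models.

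As a clarification in the same place, add that every component is oriented so that higher is better before the correlation matrix and weights are computed. If the scoring protocol already does this, a cross-reference is enough.

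The cost is two sentences and no new data. The one small drawback is that the global score would no longer be identical to any all-tests composite used in earlier trials. If that comparison matters, the 14-test version can be reported as a sensitivity analysis.

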1.2 Objectives and Hypotheses

The goal of the proposed study is to determine under randomized controlled trial conditions whether nattokinase reduces subclinical atherosclerosis and cognitive decline in healthy women and men. Our hypotheses are: 1) Compared to placebo, nattokinase will show less subclinical atherosclerosis progression and cognitive decline in healthy women and men; 2) The reduction in subclinical atherosclerosis progression and cognitive decline with nattokinase will be correlated; and, 3) The reduction in progression of subclinical atherosclerosis and cognitive decline with nattokinase will be mediated through hemostatic, fibrinolytic and hemorheological factors as well as attenuation of inflammation, monocyte activation, vascular endothelium injury and activation of vascular endothelium by circulating monocytes.

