9.6.3 Comparison of On-trial Changes in Laboratory and Lifestyle Variables

Treatment groups will be compared with respect to on-trial levels and on-trial changes in plasma insulin, lipids/CRP, hemoglobin A1c, coagulation factors, rheology parameters and inflammatory variables. Study groups will also be compared for on-trial levels and on-trial changes of other factors that might confound the analysis of primary end point differences. These will include analysis of dietary factors (e.g., total calories, and total calorie-adjusted calories from total, saturated, polyunsaturated, and monounsaturated fats, calories from protein, calories from carbohydrates, and dietary genistein, daidzein, and glycitein), physical activity, cardiovascular risk factors (including blood pressure, smoking status), and use of relevant nonstudy medications (including antihypertensive and lipid-lowering medications). For descriptive purposes, on-trial laboratory, dietary, clinical, and physical activity variables will be computed as the average of all on-trial determinations, weighted by the length of time between determinations. On-trial smoking will be compared as percentage of smokers versus percentage abstainers; average on-trial smoking levels (cigarettes per day) will also be computed for smokers as the average of all on-trial determinations as above. For all laboratory and clinical measures, a change variable will be computed at each on-trial measurement time as: on-trial value minus baseline value. Changes in laboratory and clinical variables from baseline will be compared within each treatment arm using generalized estimating equations to account for the repeated measurements over the study period; the model-specified correlation structure of the repeated measures will be determined by examination of the observed correlation structure. The test that the model intercept differs from 0 will comprise the overall test for significant change from baseline; incorporation of covariates for time periods of the study will test for differential change from baseline over the study period. Comparison of on-trial levels and changes in laboratory and clinical variables across treatment groups will also use generalized estimating equations, with an added covariate for randomized treatment group; interaction terms of treatment group-by-study time period will test whether treatment group differences vary over the study period. Compliance with the study product will be compared across treatment groups, also using generalized estimating equations as described. All analyses will be performed for the entire study sample and for the group of participants whose overall study product compliance is $>80\%$. The significance level for all analyses will be set at a two-sided $\alpha=0.05$.

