9.6.7 Ancillary Statistical Analyses

9.6.7.1 Within-Group Analyses

The effects of on-trial end point variables other than treatment modality on the per-subject rate of change in CIMT, arterial stiffness and cognition will be separately assessed. The parameters to be tested will include laboratory data (plasma insulin, lipids/CRP, hemoglobin A1c, coagulation factors, rheology parameters, inflammatory variables and nattokinase levels), clinical variables (blood pressure, body mass, waist:hip ratio, etc.), and lifestyle variables (dietary intake, physical activity, smoking, etc.). Baseline and on-trial values of these data will be collected in order to address questions of clinical significance within each treatment group such as: 1) which baseline characteristics have differential effectiveness on the rate of change in CIMT; and, 2) what is the role of changes in these variables on the rate of change in CIMT. These analyses will utilize mixed effects models and generalizing estimating equations with CIMT (arterial stiffness, cognition) as the dependent variable. Analyses will be conducted in the combined sample with a covariate included to control for treatment group. Interaction terms with treatment group will be introduced to test whether relationships between independent variables and the trial end point are of equal magnitude between the 2 study groups. Experiment-wise error rates in these analyses will be controlled. All participants contributing at least one follow-up ultrasound (or cognitive test) will be included in these analyses.

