9.6.7.3 Mediators of Treatment Efficacy

We will test the hypothesis that nattokinase treatment-related reductions in atherosclerosis and cognitive measures will be mediated through hemostatic, fibrinolytic and hemorheological factors as well as attenuation of inflammation, monocyte activation, vascular endothelium injury and activation of

vascular endothelium by circulating monocytes. We will use structural equation models to test for mediation. Observed outcome variables will be changes in CIMT (annualized change rate), stiffness (annualized change rate) or cognitive composite scores. For each of the potential mediator that shows a significant treatment effect, we will test the direct effects of randomized treatment and the indirect effects of treatment (i.e., treatment acting through the potential mediators). Bootstrapping will be used to obtain 95% confidence intervals on the direct and indirect effects; confidence intervals that exclude the value of 0 will be considered as evidence for statistical significance.

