9.6.7.4 Correlations in Atherosclerosis and Cognitive Outcome Measures

We will use mixed effects models to test the hypothesis that the reduction in subclinical atherosclerosis progression and cognitive decline with nattokinase will be correlated. The dependent variable will be each value of the CIMT (or arterial stiffness) measure at each study time point. The primary independent variables will be the 18-month and 36-month change in cognitive composites. Interaction terms of time on study with the cognitive composite change scores will test whether the rate of change in CIMT (or arterial stiffness) is associated with the change in cognition.

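### Adding the marker's baseline value to the between-arm laboratory models in 9.6.3 would gain precision at no cost, and the cognition outcome in 9.6.5.3 should be reworded as signed change

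*Combined protocol and SAP*

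**What the plan says.** **Laboratory and clinical markers (9.6.3).** For these measures, "a change variable will be computed at each on-trial measurement time as: on-trial value minus baseline value". Within each arm, a GEE is fitted: "The test that the model intercept differs from 0 will comprise the overall test for significant change from baseline". The comparison of levels and of changes across arms "will also use generalized estimating equations, with an added covariate for randomized treatment group", plus treatment-by-period interactions. No other covariate is named. Section 9.6.7.3 then states: "For each of the potential mediator that shows a significant treatment effect, we will test the direct effects of randomized treatment". It does not say which test establishes that effect.

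**Cognition (9.6.5.3).** The outcome for the three co-secondary composites is introduced with: "Absolute values of change from baseline on each cognitive endpoint will be calculated at both post-randomization cognitive follow-ups (18 and 36 months"). A GEE on repeated change follows, adjusted for CIMT stratum and the baseline cognitive value. No formula for the change is given. The hypothesis in 1.2 has a direction: "Compared to placebo, nattokinase will show less subclinical atherosclerosis progression and cognitive decline in healthy women and men".

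**Other uses of cognition.** Section 9.6.5 checks linearity of cognition against time. Section 9.6.7.1 says that effects on the "per-subject rate of change in CIMT, arterial stiffness and cognition will be separately assessed". Section 9.6.7.4 says: "The primary independent variables will be the 18-month and 36-month change in cognitive composites".

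**The concern.** For the markers, the change analysis uses baseline by subtraction and the level analysis does not use it at all. Neither uses it as a regression covariate, although the plan does so for cognition. The cost is precision, not bias. The markers carry the mechanistic hypothesis in 1.2. If the 9.6.3 comparison is also the screen for mediators in 9.6.7.3, its precision affects which mediators are examined.

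For cognition, an absolute value in the mathematical sense removes the sign. A gain and a loss of equal size become the same number, so a treatment difference could not be read as less or more decline. The only signed formula in the plan is in 9.6.3, where it is given for laboratory and clinical measures. A programmer working from 9.6.5.3 alone has no formula to set against the literal words.

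**Working it through.** The plan states no power, effect size, SD or correlation for cognition or the markers, so there is no planned figure to reproduce. Everything below except the sample size and the visit counts is an assumption.

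**Laboratory models**

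On-trial measurements, counted from the schedules in 9.2: platelet aggregation 2, inflammatory markers 4, coagulation factors and rheology 5, lipids and CRP 6, insulin and hemoglobin A1c 7, fibrinogen and PT/aPTT 8. Let m be that count. Assume unit variance at every visit, the same correlation ρ between any two visits including baseline, and no missing data. The variance contributed by each participant to the time-averaged arm contrast is:

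- level: L = (1 + (m−1)ρ)/m
- change: C = L + 1 − 2ρ
- baseline-adjusted: A = L − ρ²

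Thus L − A = ρ² and C − A = (1−ρ)². Under these assumptions adjustment never loses, apart from about one degree of freedom. Level is the better planned analysis for ρ below 0.5, and change for ρ above 0.5.

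Example, coagulation factors (m = 5) at ρ = 0.5: L = (1 + 4×0.5)/5 = 0.60; C = 0.60 + 1 − 1 = 0.60; A = 0.60 − 0.25 = 0.35; ratio 0.35/0.60 = 0.58. A test with 80% power moves to Φ((1.960 + 0.842)/√0.583 − 1.960) = Φ(1.71), about 96%.

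Adjusted variance relative to the better of L and C, and the power reached from 80%:

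| ρ | ratio, m = 2 | ratio, m = 8 | power, m = 2 | power, m = 8 |
|---|---|---|---|---|
| 0.1 | 0.982 | 0.953 | 0.807 | 0.819 |
| 0.3 | 0.862 | 0.768 | 0.855 | 0.892 |
| 0.5 | 0.667 | 0.556 | 0.929 | 0.964 |
| 0.7 | 0.800 | 0.733 | 0.879 | 0.905 |
| 0.9 | 0.933 | 0.911 | 0.826 | 0.835 |

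With the baseline value as a covariate, subtracting it from the outcome changes only its own coefficient. The level and change models then give the same treatment coefficient.

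**Cognition, if |change| were programmed**

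Input from the plan: 240 randomized. Assumed: 120 per arm, change distributed N(μ, 1), one follow-up, no covariates, two-sided 0.05, and a true benefit d = 0.363 SD, chosen because it gives 80.0% power on signed change. For |change|:

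- mean = √(2/π)·exp(−μ²/2) + μ(1 − 2Φ(−μ))
- variance = μ² + 1 − mean²

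The mean is symmetric in μ and rises with |μ|. The arms therefore tie when the placebo mean is −d/2 = −0.18 SD, not at zero.

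| Placebo mean change (SD) | Active minus placebo, mean of abs. change | Power |
|---|---|---|
| −1 | −0.212 | 58.5% |
| −0.5 | −0.090 | 19.3% |
| −0.18 | 0.000 | 5.0% |
| −0.1 | +0.023 | 6.0% |
| 0 | +0.052 | 9.9% |
| +0.5 | +0.182 | 49.9% |
| +1 | +0.276 | 71.6% |

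Simulation of 20,000 trials per row, for every row except +1, agreed to within about half a percentage point. The same benefit appears as a smaller, equal or larger |change| depending on the placebo mean. At −0.1 SD the placebo arm declines, yet the active arm shows the larger mean |change|.

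**The case against.** **Cognition.** A reader might infer that the plan intends to analyse a folded outcome. The documents do not support that. The rest of 9.6.5.3 models change and differences in change with baseline as a covariate. Section 9.6.5 treats cognition as a measurement regressed on time, 9.6.7.1 speaks of a rate of change, and 9.6.7.4 uses change as a predictor. All of this fits absolute as opposed to percent change. What stands is narrower: none of these sections gives a formula for cognition, and the words in 9.6.5.3 have a standard mathematical meaning that would produce the wrong variable.

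Nor do the power figures estimate a likely loss. They describe an analysis that is probably not intended, without the repeated measures and covariates that 9.6.5.3 plans, and their range depends on the placebo means chosen.

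A reader might also infer that score direction is undefined. It may be settled in the summary score form (9.4.1) and the analysis protocol (9.4.4), which are not in the supplied text. A citation is all that can be asked for.

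**Laboratory models.** A reader might infer that the planned comparisons are biased or invalid, or that they ignore baseline altogether. Neither holds. Unadjusted GEE is a legitimate choice under randomization, and the change comparison already uses baseline by subtraction. These markers are also neither primary nor secondary endpoints. The gain is small at very low or very high correlation, and equal correlation from week 1 to month 36 is a simplification. It is also tempting to say that 9.6.3 decides which mediators are tested, but 9.6.7.3 does not name its screening test. What stands is that the gain needs only data already scheduled, and that the plan already adjusts cognition for its baseline.

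**Conclusion.** Both points hold as modest corrections. Neither affects the co-primary CIMT and stiffness tests.

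- **Laboratory models: a free improvement in precision.** Across correlations from 0.1 to 0.9, 80% power becomes about 81–82% (0.1), 86–89% (0.3), 93–96% (0.5), 88–91% (0.7) and 83–84% (0.9). This rests on exchangeable correlation, equal variances and complete data. The plan gives no correlation, so the position within that range is unknown. An effect on mediator selection is conditional on 9.6.3 being the screen.
- **Cognition: a wording correction that removes a programming risk for all three co-secondary composites.** The text read literally cannot test the stated hypothesis; the text read in context very probably means signed, non-percent change. The direction problem does not depend on the assumed inputs, but the size of any power loss does.

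**What to change.** **9.6.3.** In the between-arm laboratory and clinical models only, add the marker's baseline value (as defined in 9.6.2) and, for consistency with 9.6.5.1 and 9.6.5.3, the CIMT randomization stratum. State that the level and change comparisons then give the same treatment coefficient, so one is reported. Leave the within-arm models unchanged, because their test of change is the intercept. State in 9.6.7.3 whether this comparison is the screen for mediators.

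**9.6.5.3.** Replace the reference to absolute values with: signed change (follow-up minus baseline composite). Use that definition in 9.6.7.3 and 9.6.7.4, and cite the scoring rule that orients the component scores in the same direction.

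**Cost.** About one sentence in each main section plus short cross-references, settled before unblinding. Baseline values and stratum are already collected, so there are no added visits, participants or assays.
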